- All subjects that complete the 8 week double-blind treatment epoch will proceed into the 8-week open-label epoch on sacubitriI/valsartan.
- At Week 8 (Visit 8), Drug accountability will be performed and all double-blind treatment medication will be returned to the site.

- Open-label sacubitril/valsartan will be dispensed at Week 8 (Visit 8) with subject's instructions **NOT** to start their open label-treatment until after completing a 36-hour wash out. All patients will have the wash out in order to maintain the blinding of the core study.

All dose levels will be available throughout the study. Dose adjustments to lower dose levels may be made at any time at both scheduled and unscheduled visits only if indicated for blood pressure control/tolerability reasons.

All study treatment assigned by the IRT will be recorded/databased in the IRT.

All dosages prescribed and dispensed to the subject and all dose changes during the study must be recorded in the IRT and on the Dosage Administration Record eCRF.

Study medication should be taken twice daily with a glass of water with or without food.

If the subject misses taking any study drug dose, he/she should take it as soon as possible and within 4 hours of the scheduled dose time. If the patient is unable to take the missed dose within 4 hours of the scheduled dose time, he/she should skip the missed dose and return back to his/her regular study drug administration schedule.

The investigator must promote compliance by instructing the subject to take the study treatment exactly as prescribed and by stating that compliance is necessary for the subject's safety and the validity of the study. The subject must also be instructed to contact the investigator if he/she is unable for any reason to take the study treatment as prescribed.

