### **5.6.2 Discontinuation of study treatment**

Subjects may voluntarily discontinue the study drug for any reason at any time.

Study drug must be discontinued under the following circumstances:

- Withdrawal of consent
- Pregnancy
- Use of prohibited concomitant medication
- Any protocol deviation that constitutes a risk to the subject
- Investigator believes that continuation of study drug may be detrimental to the subject's well-being
- Study medication may be discontinued at the investigator's discretion if any of the following occur:
  - Any severe suspected drug related AE
  - Suspected occurrence of angioedema. A subject with any signs or symptoms of clinically significant angioedema should be thoroughly evaluated by the investigator to determine if it constitutes a reason for discontinuation of study medication.

Depending on the serum potassium, blood pressure, or eGFR, subjects may need to have their study drug dose or the dose of another concomitant medication reduced or discontinued; or, if appropriate, have potentially contributing agents adjusted. Refer to appendices for treatment guidelines for hyperkalemia, hypotension or renal dysfunction, respectively.

In the case of study drug discontinuation, every effort must be made to complete an end of study visit and obtain follow up health status information for any subjects that withdraw from the

study. If the subject refuses, he/she should be contacted by telephone in place of protocol-specified visits unless the subject expressly refuses such contacts.

The investigator must notify the sponsor of any study drug discontinuation and record it on the Dosage Administration Record eCRF.

If discontinuation of study treatment occurs, the subject should NOT be considered withdrawn from the study. The subject should return to the clinic as soon as possible, after discontinuation of study drug, for an end of study visit. All assessments from the final visit (Visit 13) in the visit schedule of assessments ([Table 6-1](#)) must be completed and recorded in the eCRF. The Study Completion eCRF will also need to be completed. The investigator must determine the primary reason for the subject's premature discontinuation of study treatment and record this information in the eCRF.

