2.1.1 General definitions

Study treatment

Patients will receive either sacubitril/valsartan or enalapril during the first 8 weeks of the study. Study treatment will refer to either of these two drugs.

Baseline

The last non-missing assessment prior to or on the start date of study treatment (randomization date for patients not treated) will be used as baseline, unless otherwise specified.

Date of first administration of study treatment

Randomized treatment phase: The date of first administration of study treatment in the randomized treatment phase is defined as the first date a dose of study treatment is administered and recorded on the Dosage Administration Record - At Visit (Visit 3) electronic case report form (eCRF).

Open-label extension phase: The date of first administration of study treatment in the open-label extension phase is defined as the first date a dose of sacubitril/valsartan is administered in the open-label extension phase and recorded on the Dosage Administration Record - Summary eCRF.

Date of last administration of study treatment

Randomized treatment phase: The date of last administration of study treatment in the randomized treatment phase is defined as the last date a dose of study treatment is administered in the randomized treatment phase and recorded on the Double-Blind Phase Disposition eCRF (for patients continuing into the open-label extension phase) or the Study Completion/Discontinuation eCRF (for patients not continuing into the open-label extension phase).

Open-label extension phase: The date of last administration of study treatment in the open-label extension phase is defined as the last date a dose of sacubitril/valsartan is administered in the open-label extension phase and recorded on the Dosage Administration Record - Summary eCRF.

Study day

The study day describes the day of the assessment relative to the date of randomization.

The study day will be calculated as the difference between the date of assessment and the date of randomization plus 1. If the date of assessment is prior to the date of randomization, the study day will be negative and will be calculated as the difference between the date of the assessment and the date of randomization.

Randomized treatment phase

Assessments performed at Weeks 2, 4, or 8 (e.g., vital signs) are assigned to the randomized treatment phase for summarization purposes. Unscheduled assessments are not assigned to a phase.

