For summarization of adverse events [AEs], medications, protocol deviations, and notable vital signs and laboratory abnormalities by treatment phase, an assessment during the randomized treatment phase is defined as any assessment obtained in the following time interval:

Date of randomization (or date of first administration of study treatment, as appropriate) through the date of the Week 8 visit, inclusive.

Open-label extension phase

Assessments performed at Weeks 10, 12, or 16 (e.g., vital signs) are assigned to the open-label extension phase for summarization purposes. Unscheduled assessments are not assigned to a study phase.

For summarization of AEs, medications, protocol deviations, and notable vital signs and laboratory abnormalities by treatment phase, an assessment during the open-label extension phase is defined as any assessment obtained in the following time interval:

After the date of the Week 8 visit.

Last contact

The date of last contact will be the last visit date for each patient and will be derived by examining all visit data collected in the eCRFs.

Year, month and week

For reporting purposes, the rules below will be followed to convert a year, month and week to days.

1 year = 365.25 days

1 month = 30.3475 days

1 week = 7 days

1 day = 24 hours

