2.8.1.2 General rules for AE reporting

AE summaries will include all treatment-emergent AEs (TEAEs). TEAEs are defined as AEs starting on or after the first day of study treatment. All AEs will be listed. AEs starting prior to the first day of study treatment (non-TEAEs) will be flagged in the listings.

All TEAEs will be summarized by treatment phase as defined in Section 2.1.1.

TEAEs will be summarized by presenting the number and percentage of patients having at least one TEAE, having at least one TEAE in each primary SOC, and for each PT using MedDRA terminology. A patient with multiple occurrences of a TEAE will be counted only once in the AE category.

Separate summaries will be presented by SOC, PT and severity. A patient with multiple severities for an AE will be summarized under the worst severity recorded for the event.

Any information collected will be listed as appropriate.

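### The SAP splits safety events between phases only at the Week 8 visit date, so it has no rule for patients without that visit and labels as open-label later events in patients who never took open-label drug

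*SAP*

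**What the plan says.** SAP 2.1.1 sets two date intervals for summarizing adverse events, medications, protocol deviations and notable vital signs and laboratory abnormalities by phase. The randomized phase is "Date of randomization (or date of first administration of study treatment, as appropriate) through the date of the Week 8 visit, inclusive". The open-label phase is "After the date of the Week 8 visit", with no requirement that an open-label dose was taken and no end date.

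These intervals are used widely. SAP 2.8.1.2 states: "All TEAEs will be summarized by treatment phase as defined in Section 2.1.1". The same section gives treatment-emergent events a start bound only: "TEAEs are defined as AEs starting on or after the first day of study treatment". SAP 2.3.2 (deviations), 2.8.2 (deaths), 2.8.3 (laboratory shifts and notable values) and 2.8.4.1 (notable vital signs) are also split by phase.

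For scheduled by-visit assessments, SAP 2.1.1 assigns Weeks 2, 4 and 8 to the randomized phase and Weeks 10, 12 and 16 to the open-label phase. Unscheduled assessments get no phase.

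On early stopping of study drug, Protocol 5.6.2 says: "The subject should return to the clinic as soon as possible, after discontinuation of study drug, for an end of study visit". That visit uses the Visit 13 assessments, and Visit 13/EOS is Week 16 in Protocol Table 6-1.

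Protocol 5.5.4 has open-label drug dispensed at Week 8 but not started "until after completing a 36-hour wash out". SAP 2.1.1 separately defines the first open-label administration as "the first date a dose of sacubitril/valsartan is administered in the open-label extension phase", recorded on an eCRF. It also gives a source for the last double-blind dose date in patients who do not continue. Neither date is used to assign phase.

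**The concern.** The boundary is a visit date that some patients will not have. Without it, the randomized interval has no upper limit and the open-label interval no lower limit, and the SAP offers no fallback. The patients concerned stopped treatment early or died before Week 8, and early stoppers are plausibly the ones with tolerability events.

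The boundary is also tied to attendance rather than exposure. A patient who completes Week 8 and takes no open-label drug still contributes later events to the open-label tables.

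At stake is the labelling of events in the 8-week double-blind phase, the only randomized safety comparison. Tables could also disagree. SAP 2.3.1 counts premature discontinuations, with reasons, separately for the double-blind and open-label phases. The table of adverse events leading to discontinuation (SAP 2.8.1.3) is split by the Week 8 date. One patient could therefore be a double-blind discontinuation in the first and be placed elsewhere, or nowhere, in the second.

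**Working it through.** **1. Apply the date rule to each type of patient.**

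| Patient | Week 8 date | Randomized interval | Open-label interval |
|---|---|---|---|
| Continues into open label | Yes | Defined | Defined; starts the day after the visit |
| Stops drug or dies before Week 8 | Normally none | No upper bound | No lower bound |
| Attends Week 8, takes no open-label drug | Yes | Defined | Every later event counts as open-label |

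Protocol 5.6.2 allows telephone contact on the visit schedule for patients who do not attend, but neither document says that such a call serves as the Week 8 visit.

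**2. Apply the visit rule to the early end-of-study visit.** If the visit is stored as Visit 13/Week 16, its scheduled laboratory values and vital signs are labelled open-label although no open-label drug was taken. Protocol Table 6-1 also allows unscheduled-visit assessments when a patient withdraws early. If the visit is stored that way, the by-visit rule gives it no phase.

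**3. Illustrate the number of patients.** The plan's own figure comes first. Inputs from Protocol 9.8 and SAP 3 are: difference 5000, SD 7400, two-sided 0.05, 90% power, 20% drop-out and 10% non-evaluable.

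- Normal approximation: n per arm = 2 × (1.960 + 1.282)² × (7400/5000)² = 46.0, rounded up to 47. The total is 94, and 94/0.70 = 134.3.
- With the t distribution, 47 per arm gives 89.99% power, so 48 are needed. The total is 96, and 96/0.70 = 137.1.
- The planned 136 lies between these. At 136 × 0.70 = 95.2 evaluable patients, power is 90.4% (t distribution).

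So 136 is reproduced, with the 20% acting as an allowance for loss from a Week 8 analysis. Assume that all of it falls before the Week 8 visit:

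- 0.20 × 136 = 27.2, about 27 patients (0.20 × 68 = 13.6 per arm)
- 0.10 × 136 = 13.6, about 14 patients
- 0.30 × 136 = 40.8, about 41 patients

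**4. Size the wash-out effect.** Protocol 5.5.4 keeps patients on their blinded dose through the evening before Visit 8 (Day 56 in Table 6-1). SAP 2.1.1 counts the visit date as randomized phase. Assume dosing at 08:00 and 20:00, with open-label drug started at the first slot after 36 hours.

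- Last dose Day 55 at 20:00, plus 36 h = Day 57 at 08:00. No full calendar day is mislabelled; only the 8 hours of Day 57 before that dose are.
- If the 36 hours run instead from a midday Day 56 visit, they end at 00:00 on Day 58 and the first slot is Day 58 at 08:00. A Day 56 dose at 20:00 gives the same slot. One full calendar day (Day 57) is then labelled open-label before any open-label drug.

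The result is 0 to 1 calendar day per continuing patient, and more only if open-label dosing is delayed.

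**The case against.** The strongest reply is that this is a drafting gap that any competent programmer would close. The SAP names a disposition form for the double-blind phase and a completion/discontinuation form for patients who do not continue, so phase status can be known without a Week 8 date. All adverse events are listed, and SAP 2.8 plans no inferential safety analysis. That is fair, and it limits the consequences. It does not supply the rule: placing such events in the randomized phase is sensible but not written. For patients who attend Week 8 and stop, the rule as written gives a definite and wrong label.

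A second objection is that sending all events of non-continuers to the randomized phase would be unbounded and could charge late events, possibly on other therapy, to blinded drug. Protocol 7.1 largely answers this by ending the adverse event period at the end-of-study visit. Serious events are reportable for longer (Protocol 7.2.2), so anything later needs its own label.

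A reader might also infer stronger points that the documents do not support:

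- *Missing dates will push all early stoppers' events into open label in SAS.* That depends on code that the SAP does not describe. The SAP leaves the case undefined.
- *The whole 36 hours (1.5 days) is misassigned in every patient.* The scheduled last blinded dose is the evening before the visit, and the visit day counts as randomized phase, so most of the wash-out falls on the correct side.
- *The wash-out is the angioedema risk window.* Protocol 3.2 and 3.6 place the added risk in receiving both an ACE inhibitor and sacubitril/valsartan, and present the wash-out as the measure that reduces it.

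**Conclusion.** The concern holds as a defect in the phase definition. Applied as written, SAP 2.1.1 cannot place the events of patients without a Week 8 visit. It also mislabels as open-label every later event in patients who reach Week 8 but take no open-label drug.

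The size is illustrative. About 27 of 136 patients (14 to 41 at 10% to 30%) rests on the assumption that the planned drop-out all occurs before Week 8; the documents give no count of patients expected to lack that visit. Nor would the randomized comparison be emptied, as a reader might fear: at 20%, about 109 of 136 patients (136 − 27) still have a usable boundary. Power, alpha and sample size do not change. The wash-out contribution is minor, given prompt open-label dosing.

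It should be corrected because these intervals drive most safety tables and the early stoppers belong in the randomized comparison.

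**What to change.** Amend SAP 2.1.1 as follows:

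- **Randomized phase:** from randomization (or first dose, as appropriate) to the day before the first open-label dose date.
- **Open-label phase:** from the first open-label dose date, as SAP 2.1.1 already defines it.
- **Patients with no open-label dose:** assign all events through the end-of-study visit to the randomized phase, together with the assessments made at an early end-of-study visit, however that visit is numbered. Show any later events in a separately labelled off-treatment period.

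A date-level split still counts an event on the first open-label dosing day as open-label even if it came before the dose. In the scheduled wash-out case (open-label start on Day 57) the boundary therefore does not move. The gain lies in patients without a Week 8 visit, those who do not continue, and those who start open label later.

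The cost is SAP wording and the matching table specifications, settled before unblinding. No new data are needed: the first open-label dose date and the visit dates are already collected.

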2.2 Analysis sets

The following analysis data sets will be used in the analyses:

Randomized Set (RS): The RS will consist of all randomized patients.

Full Analysis Set (FAS): The FAS will consist of all randomized patients with the exception for those patients who have not been qualified for randomization and have not received study treatment, but have been inadvertently randomized into the study. Following the intent-to-treat principle, patients will be analyzed according to the treatment to which they were assigned at randomization. Efficacy variables will be analyzed based on the FAS as the primary set.

Safety Set (SS): The SS will consist of all randomized patients who have received at least one dose of study treatment. Patients will be included in the analysis according to the treatment actually received. The SS will be used for the analyses of safety variables.

2.2.1 Subgroup of interest

The following subgroups will be analyzed for the primary objective:

1. Age groups (<65, \geq 65 years; and <75, \geq 75 years)
2. Baseline ejection fraction categories (<25%, 25% - <35%, \geq 35%)
3. Baseline quartiles of mean activity counts during the most active 30 minutes of the patient's day (counts) (mean of data collected each day during Week -1) (based on FAS)
4. New York Heart Association (NYHA) classification [best value during the past month prior to screening visit] (II, III)
5. Prior HF hospitalization (No, Yes)
6. History of diabetes (No, Yes)
7. Baseline body mass index (BMI) categories (<25, 25 - <30, \geq 30 kg/m²)
8. Baseline quartiles of mean activity during the daily active period (counts/minute) (mean of data collected each day during Week -1)
9. Baseline sleep efficiency categories (<70%, 70-90%, >90%)
10. Baseline apnea hypopnea index (AHI) 4% categories (<15, \geq 15 events/hour)
11. Baseline quartiles of the Kansas City Cardiomyopathy Questionnaire (KCCQ) overall summary score

See Section 2.5 for further details on the primary objective.

2.3 Patient disposition, demographics and other baseline characteristics

2.3.1 Patient disposition

All patients will be used for the summary of patient disposition. The following categories will be summarized:

- Number of patients who were screened
- Screening phase disposition
 - Completed
 - Adverse event
 - Death
 - Pregnancy
 - Screen failure
 - Study terminated by sponsor
 - Technical problems
 - Lost to follow-up
 - Physician decision
 - Patient/guardian decision

- Number of patients who were randomized
- Number and percentage of patients who were treated
- Number and percentage of patients who achieved dose level 3
- Number and percentage of patients who did not achieve dose level 3
- Reason for not achieving dose level 3
 - Hyperkalemia
 - Symptomatic hypotension
 - Renal dysfunction
 - Angioedema
 - Other adverse event
 - Unrelated to study treatment tolerability
- Number and percentage of patients who completed study treatment
- Number and percentage of patients who prematurely discontinued study treatment during the double-blind phase
 - Treatment unblinded by site (No, Yes)
- Number and percentage of patients who prematurely discontinued study treatment during the open-label phase
- Reason for premature discontinuation of study treatment (during double-blind phase and open-label phase, separately)
 - Adverse event
 - Death
 - Pregnancy
 - Study terminated by sponsor
 - Technical problems
 - Lost to follow-up
 - Physician decision
 - Patient/guardian decision
- Number and percentage of patients who continued into the open-label phase
- Study duration in months $[(date\ of\ last\ contact/death - date\ of\ randomization +1)/30.3475]$

Additionally, listings of inclusion/exclusion criteria, screening/double-blind/open-label phase disposition and study treatment disposition will be provided.

2.3.2 Protocol deviations

The number and percentage of patients with protocol deviations by category will be summarized by treatment phase (see Section 2.1.1 treatment phase definitions). Additionally, a listing of protocol deviations during the study will also be presented. The RS will be used.

2.3.3 Demographics and other baseline characteristics

Descriptive summaries and/or listings will be provided for demographics, baseline characteristics and disease history. The number and percentage (categorical variables) and descriptive statistics (continuous data) for the information below will be summarized by treatment group for both the randomized treatment and open-label extension phases.

The RS and FAS will be used.

Demographics and baseline characteristics

Demographic variables include:

- Age (years), age group (<65, \geq 65 years; and <75, \geq 75 years)
- Sex (Male, Female)
 - Child bearing status (Able to bear children, Post-menopausal, Sterile)
- Race (Caucasian, Black, Asian, Native American, Pacific Islander, Other, Unknown)
- Ethnicity (Hispanic or Latino, Not Hispanic or Latino, Unknown)

[figure not shown]
General baseline characteristic variables include:

- Height (cm)
- Weight (kg)
- BMI (kg/m^2) [$= \text{weight} (\text{kg})/\text{height} (\text{m}^2)$ from Screening Visit 1]
 - BMI categories (<20, 20 - <25, 25 - 30, \geq 30 kg/m^2)
- Estimated Glomerular Filtration Rate (eGFR) ($\text{ml}/\text{min}/1.73 \text{ m}^2$)
 - eGFR categories (<45, 45 - <60, \geq 60 $\text{ml}/\text{min}/1.73 \text{ m}^2$)

Key actigraphy [REDACTED] baseline characteristic variables include:

- Mean activity counts during the most active 30 minutes of the patient's day (counts)
- Mean activity counts during the most active 6 minutes of the patient's day (counts)
- Mean activity during sleep (counts/minute)
- Mean activity during the daily active period (counts/minute)

Disease history

Disease history variables, as collected on the Heart Failure History eCRF at screening, include:

- NYHA classification [best value during the past month prior to screening visit] (I, II, III, IV)
- Primary HF etiology (Ischemic, Non-ischemic)
 - Non-ischemic etiology (Hypertensive [No, Yes], Diabetic [No, Yes], Alcoholic [No, Yes], Myocarditis [No, Yes], Peripartum [No, Yes], Drug induced [non-chemotherapy] [No, Yes], Chemotherapy [No, Yes], Idiopathic Other [No, Yes], Valvular heart disease [No, Yes], Other [No, Yes])
- Myocardial infarction (No, Yes)
- Coronary revascularization (No, Yes)
 - Coronary revascularization type (Percutaneous coronary intervention [PCI], Coronary Artery Bypass Graft [CABG])
- Prior heart failure hospitalization (No, Yes)
 - Number of heart failure hospitalizations in the last 12 months
- Most recent ejection fraction (%)
 - Ejection fraction categories (<25%, 25% - <35%, ≥35%)
 - Method used (Magnetic Resonance Imaging [MRI], Echocardiography, Nuclear [SPECT/PET/MUGA], Ventriculogram, Other)
- ACE inhibitor intolerant (No, Yes)
- Known history of diabetes mellitus (No, Yes)
 - Controlled by: Insulin (No, Yes), Oral anti-diabetic agent (No, Yes), GLP-1 agonist (No, Yes), Diet only (No, Yes)

Cardiovascular history

Cardiovascular history will be summarized. The following disease information will be collected:

- Hypertension (No, Yes, Unknown)
- Transient Ischemic Attack (TIA) (No, Yes, Unknown)
- Stroke (No, Yes, Unknown)
- Peripheral vascular disease (No, Yes, Unknown)
- Chronic Kidney Disease (CKD) stage (CKD stage 1 [eGFR ≥90], CKD stage 2 [eGFR 60 - 89], CKD stage 3 [eGFR 30 - 59], CKD stage 4 [eGFR 15 - 29], CKD stage 5 [eGFR <15 or dialysis], No CKD)

- Arrhythmia (No, Yes, Unknown)
 - Arrhythmia type (Atrial fibrillation, Atrial flutter, Supraventricular tachycardia, Ventricular tachycardia)
- Pacemaker/Implantable Cardioverter Defibrillator (ICD) (No, Yes, Unknown)
 - Device type (Pacemaker, Cardiac resynchronization therapy - no ICD [CRT-P], Cardiac resynchronization therapy - with ICD [CRT-D], ICD only [single/dual chamber], Unknown)
- Moderate to severe valvular heart disease (No, Yes, Unknown)
 - Valvular heart disease type (Mitral regurgitation, Aortic regurgitation, Aortic stenosis, Tricuspid regurgitation, Other)
- Prior valvular surgery (No, Yes, Unknown)
 - Valvular surgery type (Mitral, Aortic, Tricuspid, Pulmonic)

Non-cardiovascular medical history

Non-cardiovascular medical history will be summarized and listed. The summary will be presented by primary system organ class (SOC), preferred term (PT) and treatment group for both the randomized treatment and open-label extension phases. Non-cardiovascular medical history will be coded using Medical Dictionary for Regulatory Activities (MedDRA) terminology (v19.0 or later).

Surgeries and Medical Procedures

Surgeries and medical procedures will be listed. Surgeries and medical procedures will be coded using MedDRA terminology (v19.0 or later).

